3.7 Sample Storage

Blood and urine samples will be kept frozen at -60 degrees Centigrade or colder once the initial processing has taken place. Stool samples will be kept refrigerated at 4 degrees C until processed. Samples shall be stored in appropriate freezers in the PI's laboratory, located in a restricted area inside the UAMS IOA building. Said freezers are monitored continuously for proper temperature and working condition. Samples will be destroyed only after all data has been analyzed and reported to the sponsor. All blood samples shall be identified using a

unique study acronym. None of a subject's personal identifiers shall be present on any biological sample. Urine samples collected during visits 2 and 14 will be discarded immediately after performing the dipstick test for proteinuria.

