3.1 Study Visits

Visit 1: subjects will come to the UAMS IOA 3rd floor for informed consent discussion. Once consent is obtained, study staff will administer and score the SLUMS test for dementia. If subjects score >20 , subsequent study procedures will be performed. A medical history and list of current medications will be obtained (printed from Epic if they are a UAMS patient). Subject height, weight, body temperature and blood pressure will be measured. A blood sample will be drawn (approx. 15 mL) for criteria-related tests if recent results are not available from their medical record. A brief training session will take place where subjects will be introduced to the

isokinetic dynamometer (Cybex) machine and how it is used at the testing visits. They will undergo a practice test on one leg.

A physical exam will be performed at this visit or at visit 2. Based upon the results of the screening blood sample, visit 2 will be scheduled.

Visit 2: Subjects must come to this visit having fasted overnight. They will be asked about any adverse events since last visit. A fasting blood sample (~30 mL) will be drawn to determine baseline values (tests listed below), and a snack will be provided and coffee offered. A urine sample will be collected for dipstick proteinuria. Subjects will be asked to provide a stool sample, but if unable at this visit, they can take home a sample collection kit to use. They will be instructed to collect the stool sample at home on the day of Visit 2 or at UAMS. Subjects will be provided with a drink containing 30mg of a stable isotope of creatine (D-3, Cambridge Isotopes Laboratory, Tewksbury, MA) dissolved in water. They will be asked to collect 3 separate urine samples over the next 72 hours at approximately 24-hour intervals, place them into their freezer, and return them to UAMS at their next visit.

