If not performed at visit 1, the physical exam will be performed at this visit. Randomization will be performed as mentioned below. The following assessments will be performed: functional (6-minute walk distance), SF-36 health questionnaire, a whole-body DEXA scan for lean mass measurement, strength (Cybex testing of maximal voluntary contraction of each leg; bilateral hand grip strength). Subjects will be provided with forms and training for recording their dietary intake over a 3-day period during the next week. Study staff will dispense approximately 10 days' worth of study product and a consumption diary for subjects to complete after ingesting each dose. Future visits will be scheduled.

Visits 3-7: Subjects will come to the IOA weekly to return their urine samples, empty supplement containers and consumption diary. They will be asked about any adverse events since last visit. Study staff will dispense more study product and a consumption diary.

Visit 8: Subjects will be asked about any adverse events since last visit. They will return their empty supplement containers and consumption diary. In no particular order, the following assessments will be performed: strength (Cybex testing of maximal voluntary contraction of

each leg; bilateral hand grip strength), functional (6-minute walk distance), SF-36 health questionnaire. Study staff will dispense more study product, a consumption diary, and another 3-day diet diary.

Visits 9-12: Subjects will come to the IOA weekly to return their empty supplement containers and consumption diary. They will be asked about any adverse events since last visit. Study staff will dispense more study product and a consumption diary.

Visit 13: Subjects will come to the IOA to return their empty supplement containers and consumption diary. They will be asked about any adverse events since last visit. Study staff will dispense more study product and a consumption diary. Subjects will be provided with a drink containing 30mg of a stable isotope of creatine (D-3, Cambridge Isotopes Laboratory, Tewksbury, MA). They will be asked to collect 3 separate urine samples over the next 48 hours at approximately 24-hour intervals and return them to UAMS at their next visit. Subjects will be issued a stool sample collection kit to use just prior to visit 14 and another 3-day diet diary.

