7.6 Urine analyses

Urine samples will be analyzed for the presence of D3-creatinine (mass spectroscopy in PI's lab) and unlabeled creatinine (Labcorp, Dallas, TX). Subjects will be sent home with 3 labelled urine collection containers to use at appropriate intervals after ingestion.

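### No urine is taken before the second D3-creatine drink at Visit 13, so label left from the Visit 2 dose cannot be subtracted and would understate final muscle mass

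*Combined protocol and SAP*

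**What the plan says.** Section 3.1 uses the same words for the tracer at Visit 2 and at Visit 13: "Subjects will be provided with a drink containing 30mg of a stable isotope of creatine". After the Visit 2 drink, subjects are to "collect 3 separate urine samples over the next 72 hours at approximately 24-hour intervals". After the Visit 13 drink, they are to "collect 3 separate urine samples over the next 48 hours at approximately 24-hour intervals".

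Section 7.6 states "Urine samples will be analyzed for the presence of D3-creatinine", with unlabelled creatinine measured as well. It places collection after the dose: "Subjects will be sent home with 3 labelled urine collection containers to use at appropriate intervals after ingestion". Section 5.1 says that the labelled creatinine serves to determine skeletal muscle mass, and cites reference 14, whose title describes a creatine dilution method.

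The Table of Events shows a clinic urine sample at Visits 2 and 14 only. Its footnote places the three-day isotope collections at home between visits. Section 3.7 says of the clinic urine: "Urine samples collected during visits 2 and 14 will be discarded immediately after performing the dipstick test for proteinuria". No section describes subtracting background or residual label.

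**The concern.** In a dilution method, the pool is estimated as dose divided by enrichment, so extra label makes the pool look smaller. At Visit 2 the subject has had no study tracer. At Visit 13, some label from the first drink may still be in the creatine pool, and the post-dose samples cannot show which dose it came from.

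The error can fall only on the second measurement. The baseline covariate in Section 7.1 therefore does not remove it, and neither does a change score. Section 7.1 applies the model to each parameter, and Section 7.2 allows a time effect to be tested within each group. Carry-over could then be reported as loss of muscle over 12 weeks in both arms.

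**Working it through.** The documents state no effect size, standard deviation, power or turnover rate for D3-creatine muscle mass, so there is no figure of the plan's own to reproduce. The check uses the visit schedule and a simple dilution model.

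**Interval between doses.** Visits are weekly (for example, "Visits 9-12: Subjects will come to the IOA weekly to return their empty supplement containers and consumption diary"). Visit 2 to Visit 13 is 13 − 2 = 11 intervals, or 11 × 7 = 77 days. If Visit 2 is the week −1 assessment mentioned in Section 1.0, the interval is 12 weeks, or 84 days.

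**Bias.** Let D be the dose (30 mg both times), P the true pool at Visit 13, and r the residual first-dose label as a fraction of D.

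- Observed enrichment = D(1 + r)/P
- Estimated pool = D ÷ [D(1 + r)/P] = P/(1 + r)
- Understatement = 1 − 1/(1 + r) = r/(1 + r)

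**Size.** The daily loss rate k is an assumption, shown as a range. With first-order loss, r = exp(−k × days).

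| Assumed k per day | r at 77 days | Final mass too low by | r at 84 days | Final mass too low by |
|---|---|---|---|---|
| 0.05 | 0.021 | 2.1% | 0.015 | 1.5% |
| 0.03 | 0.099 | 9.0% | 0.081 | 7.4% |
| 0.02 | 0.214 | 17.7% | 0.186 | 15.7% |
| 0.01 | 0.463 | 31.6% | 0.432 | 30.2% |

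Expressed as half-lives, with r = 2^(−11/half-life in weeks), assumed values of 1, 2, 4, 6 and 8 weeks give understatements of about 0%, 2.2%, 12.9%, 21.9% and 27.8% at 11 weeks.

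**Effect on the comparisons.** Take invented true masses: 25 units at baseline in both arms, then 25 (control) and 26 (active) at the end, with r = 0.15 in both arms.

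- Control: 25/1.15 = 21.74, an apparent change of −3.26 where the true change is 0.
- Active: 26/1.15 = 22.61.
- Arm difference: 22.61 − 21.74 = 0.87, where the true difference is 1.

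With equal r, the within-group change is wrong in both arms and the arm difference shrinks by 1/(1 + r), but no false arm difference appears. In this model r depends on k and the interval, not on P, so a change in muscle mass alone leaves the proportional bias the same in both arms.

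**After the fix.** Enrichment just before the second drink is Dr/P. Subtracting it from D(1 + r)/P leaves D/P, and the estimated pool returns to P.

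**The case against.** - **Size.** The documents say nothing about creatine turnover. A half-life of one week leaves almost no carry-over, and nothing in the protocol favours a slower rate. This stands: a reader might infer from the table that a large bias is expected, but only its direction and the inability to correct it follow from the documents.
- **The discarded urine.** A reader might infer that Section 3.7 is the fault. It is not. The Visit 14 sample follows the second dose. The Visit 2 sample, if voided before the drink, contains no study tracer and could show only assay or natural background. Such background would be present at both time points and would largely cancel in the change. Keeping both samples would leave carry-over untouched.
- **Bias between arms.** A reader might infer that a supplement effect on muscle mass would itself make the bias differ by arm. The model does not support that. Only a difference in creatine turnover would, and the documents do not address one.
- **Collection wording.** Three samples over 48 hours at 24-hour spacing would fit times 0, 24 and 48 hours. However, no pre-drink sample is stated, Section 7.6 puts the containers after ingestion, and the collection is done at home after a drink given in the clinic. This does not rescue the plan.
- **The cited method.** Reference 14 may deal with background, which cannot be checked here. Direct subtraction would still need a measurement just before the second dose, and none is planned.
- **Importance.** D3-creatine muscle mass is absent from the hypotheses (Section 2.0), from Table 4, and from the secondary endpoints named in Section 7.3. DEXA lean mass is measured separately at Visits 2 and 14. This stands and limits the weight of the point.

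**Conclusion.** The point holds as a gap in the Visit 13 procedures: the same tracer is given twice and no urine is taken before the second drink. Any residual label lowers estimated final muscle mass by r/(1 + r), and this cannot be corrected afterwards from the samples planned.

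Under assumed losses of 5%, 3%, 2% or 1% per day over 77 days, the understatement is about 2%, 9%, 18% or 32%. These figures rest on a single pool, equal doses, first-order loss and a loss rate that the documents do not give; a faster rate would make the bias negligible. The damage is mainly to the within-group time trend. The randomised comparison is attenuated, and is falsely shifted only if turnover differs by arm. The documents do not support reading this as a threat to the functional or quality-of-life conclusions. It is an inexpensive improvement to a supporting measure.

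**What to change.** Collect one spot urine at Visit 13 before the drink. Assay it for D3-creatinine and unlabelled creatinine, and subtract its enrichment from the post-dose values before computing final muscle mass. Amend Section 3.1 (Visit 13), Section 7.6 and the Table of Events, and state the subtraction in Section 7.6. If the residual proves negligible, the sample will show that.

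The cost is one spot urine at a visit already scheduled and one further set of assays per subject. A pre-drink aliquot at Visit 2 is optional: it would document background but does not address carry-over.

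In the same amendment, reconcile the collection wording: 72 hours after the Visit 2 drink against 48 hours after the Visit 13 drink in Section 3.1, and the statement in Section 5.1 that the first isotope urine is collected between Visits 1 and 2, although the first drink is given at Visit 2.

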4.0 Study Population

Subjects will be recruited using these methods: 1) past subjects that indicated they wanted to be contacted about future studies will be called by study staff to elicit their interest in this study, and 2) the PI will refer potential subjects from her UAMS clinic population to study staff who will then contact the referrals via phone. Once a potential subject has agreed to come to UAMS for an informed consent discussion, an appointment will be made for them to meet with study staff in the research area of the 3rd floor of the Reynolds Institute at UAMS. This study will enroll up to 80 subjects aged 60-89 years inclusive.

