In a pilot study 18 overweight/obese subjects with heart failure (all exceeded 40% body fat) were studied. Nine subjects received 12 weeks of dietary supplementation with 20 g of whey protein consumed daily, while the other nine were controls. Consistent with the acute data showing a limited stimulation of muscle protein synthesis with dietary amino acids in the profile of whey protein in even healthy elderly (i.e., anabolic resistance, Figure 1), supplementation with whey protein failed to improve functional performance. The lack of a demonstrable effect of whey is consistent with the diminished responsiveness to the stimulation of muscle protein synthesis by whey protein in heart failure (10). In contrast, a 2016 UAMS pilot study found that the EAA mixture is better at overcoming anabolic resistance than Ensure Heart Health (see below).

[figure not shown]

Figure 5. Average rates of Protein synthesis, breakdown and net balance between synthesis and breakdown after consumption of Ensure Heart or UpBeat. **significantly different from fasted state ($p < 0.005$); ***significantly different from fasted state ($p < 0.0005$); ## significantly different between treatments ($p < 0.005$).

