3.5 Blinding

This is a double-blinded study. EAA mixture will be provided by Prinova Inc. (Carol Stream, IL). Placebo will be purchased from online or local sources (Pure Protein website, Wal-Mart, etc.). Product containers will be coded so that only the unblinded study staff will know product

identity. After all study visits have been performed and all data entered into a database, the blind will be broken. Although the study products differ in taste, subjects will not be told which products are offered in which flavors.

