3.6 Study Products

The active study product is 9g twice a day of EAA mixture, a proprietary formula of Essential Blends, LLC (Fairbanks, AK). Product is a blend of amino acids, flavorings, caffeine and sweeteners (see Appendix) in powder form; packaged in 200g sealed containers. Subjects will dissolve 1 scoop of supplement into ~7 ounces of water and stir/shake until fully dissolved. They will be provided with shaker cups free of charge. Servings will be ingested between meals so that they ingest 2 servings per day. EAA mixture is currently available in only one flavor (lemon/lime).

The placebo product is 9g twice a day of Pure Protein 100% Whey protein (Worldwide Sport Nutritional Supplements, Inc., Bayport, NY). Unblinded study staff will repackage this product into 200g sealed containers which contain the appropriate scoops. See appendix for product information. Subjects will dissolve 1 scoop of supplement into ~7 ounces of water and stir/shake until fully dissolved. Servings will be ingested between meals so that they ingest 2 servings per day.

Subjects will be asked to save empty containers and return them to the study site for accountability purposes. Storage of both products is in a dry area at room temperature. Containers will be labelled identically, with the only difference being the study product code (A or B); the key to which is known only to the unblinded study staff until blinding has been broken at the end of data analysis.

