4.2 Exclusion Criteria

- Allergic to milk or soy products
- Hemoglobin <10 g/dL
- eGFR < 30
- Inability to perform strength and/or functional assessments
- Myocardial infarction in the past 6 months
- Unstable angina
- Moderate-severe heart valve disease
- Infiltrative, restrictive or hypertrophic cardiomyopathy
- Dementia –determined by a SLUMS score of <20

- Currently has inflammatory bowel disease
- Received chemotherapy or radiation therapy within the past 12 months
- Currently undergoing tube feeding
- Currently receiving palliative care for end-of-life circumstance
- Unwilling to refrain from using non-study protein/amino acid supplements during their participation in this study
- If deemed medically unstable by the study physician for any other reason.

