11.0 Appendices

11.1 Study Product Information

EAA mixture

His	3.5%
Ile	7.1%
Leu	14.3%
Lys	6.0%
Met	3.3%
Phe	8.8%
Thr	5.3%
Trp	1.4%
Val	9.25%
Glutamine	1.2%
Carnitine	2.9%
Nicotinamide	1.5%
Vitamin C	1.5%
Caffeine	0.6%
Sucralose and other flavorings and preservatives	28.3%

Placebo: Pure Protein – Vanilla Creme flavor

Directions: For adults, take one (1) scoop (39 g), one to two times daily. For maximum muscle support consume 1-2 scoops twice per day, with at least 1-2 scoops taken immediately after exercise.

Nutrition Facts

Serving Size 1 Scoop (39g)
Servings Per Container about 23

Amount Per Serving		
Calories 150		Calories from Fat 25
		%Daily Value*
Total Fat 2.5g		4%
Saturated Fat 1g		5%
Trans Fat 0g		
Cholesterol 80mg		27%
Sodium 100mg		4%
Potassium 160mg		5%
Total Carbohydrate 8g		3%
Dietary Fiber 0g		0%
Sugars 2g		
Protein 25g		50%
Vitamin A 0%		Vitamin C 0%
Calcium 20%		Iron 0%
Phosphorus 10%		Magnesium 4%

*Percent Daily Values are based on a 2,000 calorie diet. Your daily values may be higher or lower depending on your calorie needs:

	Calories:	2,000	2,500
Total Fat	Less than	65g	80g
Sat Fat	Less than	20g	25g
Cholesterol	Less than	300mg	300mg
Sodium	Less than	2,400mg	2,400mg
Potassium		3,500mg	3,500mg
Total Carbohydrate		300g	375g
Dietary Fiber		25g	30g
Protein		50g	65g

Calories per gram:
Fat 9 • Carbohydrate 4 • Protein 4

INGREDIENTS: Protein Blend (Ultrafiltered Whey Protein Concentrate [which contains Beta-lactoglobulin, Alpha-lactalbumin and Glycomacropeptides], Microfiltered Whey Protein Isolate), Maltodextrin, Natural and Artificial Flavors, Cellulose Gum, Soy Lecithin, Xanthan Gum, Dicalcium Phosphate, Calcium Carbonate, Acesulfame Potassium, Sucralose.

Contains milk and soy ingredients.

Typical Amino Acid Profile (milligrams per 39 g scoop**)			
Essential Amino Acids		Nonessential Amino Acids	
Histidine	490 mg	Alanine	1,139 mg
Isoleucine	1,460 mg	Arginine	640 mg
Leucine	2,531 mg	Aspartic Acid	2,980 mg
Lysine	2,127 mg	Cysteine	601 mg
Methionine	562 mg	Glutamic Acid	3,919 mg
Phenylalanine	808 mg	Glycine	444 mg
Threonine	1,783 mg	Proline	1,415 mg
Tryptophan***	485 mg	Serine	1,299 mg
Valine	1,376 mg	Tyrosine	728 mg

***L-tryptophan is naturally occurring, not added.
**approximate values

©2014 Carefully Manufactured by
Worldwide Sport Nutritional Supplements, Inc.
Bayport, NY 11705

For questions or reorders call:
[name]
or visit our website at
www.pureprotein.com

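### Past subjects may be recruited, but nothing excludes people who have already consumed the EAA mixture, for whom withholding the flavour cannot protect the blind

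*Combined protocol and SAP*

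**What the plan says.** Recruitment (Section 4.0) has two routes. In one, "past subjects that indicated they wanted to be contacted about future studies will be called by study staff". In the other, "the PI will refer potential subjects from her UAMS clinic population to study staff". The earlier studies are not named.

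Earlier local use of the product (Section 1.0): "a 2016 UAMS pilot study found that the EAA mixture is better at overcoming anabolic resistance than Ensure Heart Health". The number of subjects, the length of exposure and the flavour served are not given.

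Eligibility (Sections 4.1 and 4.2): no item concerns earlier consumption of the EAA mixture or earlier participation in a study of it. The one supplement item excludes a person who is "Unwilling to refrain from using non-study protein/amino acid supplements during their participation in this study".

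Blinding (Section 3.5): "Although the study products differ in taste, subjects will not be told which products are offered in which flavors". Section 3.6 gives lemon/lime as the only flavour of the EAA mixture, and Section 11.1 lists the placebo whey as "Vanilla Creme flavor". Containers carry identical labels apart from an A or B code.

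**The concern.** Coding the containers hides the label but not the taste. For taste, the stated protection is that the subject does not know which flavour belongs to which product. Someone who drank the EAA mixture in an earlier study may already have that knowledge, and the plan allows such a person to be called, found eligible and randomised.

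The outcomes are open to the subject's belief about treatment. Hypothesis 2 rests on the SF-36, which is self-reported. Hypothesis 1 rests on physical function, measured by the 6-minute walk, hand grip and Cybex leg tests, all of which depend on effort. A subject who believes they are on the active product may try harder or rate their health better, and one who believes they are not may do the reverse. Both would widen the difference between arms in favour of the EAA mixture.

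**Working it through.** No figure in the plan is in dispute. The check is whether any provision stops a prior EAA consumer from entering the trial and recognising the product.

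1. **Can such a person be on the call list?** Section 4.0 draws on past subjects without limiting which studies they came from. Section 1.0 places an EAA study at the same institution in 2016. So it is possible; the documents do not show that it will happen, or how often.

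2. **Does eligibility remove them?** Section 4.1 covers age, BMI, ethnicity and heart failure. In Section 4.2 the only item on supplements looks forward and concerns non-study products. Past consumption of the EAA mixture triggers no exclusion.

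3. **Does the blinding procedure cover them?** Identical, coded containers do not conceal a lemon/lime drink from someone who knows it, or disguise a vanilla drink as it. Non-disclosure of flavour works only for subjects who do not already know.

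4. **Does the design or analysis absorb the effect?** Baseline is measured at Visit 2, the visit at which product is first dispensed (Section 3.1). Recognition comes after baseline, so the baseline covariate in Section 7.1 cannot adjust for it. Randomisation is stratified by gender only (Section 3.4), and no model term represents prior exposure. Balancing prior consumers across arms would not help either, because the effect of recognition arises after allocation and can differ in sign between arms.

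5. **How large could it be?** Let f be the share of each arm that recognises the product, u the upward shift among recognisers on the EAA mixture, and d the downward shift among recognisers on placebo. Then

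 bias in the arm difference = f × u + f × d = f × (u + d).

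 The documents give none of f, u or d. As an illustration on assumed values only, take u = d = 30 in the units of the 6-minute walk row of Table 4:

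 | Assumed f | Recognisers per arm of 30 | Bias = f × 60 | Relative to the Table 4 difference of 105.1 |
 |---|---|---|---|
 | 0 | 0 | 0 | 0% |
 | 0.10 | 3 | 6 | 6 / 105.1 = 5.7% |
 | 0.20 | 6 | 12 | 12 / 105.1 = 11.4% |

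 The table shows how the bias scales. It is not an estimate. No such scaling is possible for the SF-36, because Table 4 gives it no hypothesised difference or standard deviation.

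**The case against.** **Past subjects may supply few or no EAA consumers.** Section 4.0 is a numbered list of two sources. A reader might infer that past subjects are called first or will make up most of the sample, but the text gives no order of calling and no proportions. It names no earlier study. Section 1.0 does not say how many took part in the 2016 pilot, whether they had heart failure or whether they would be eligible now. Its figure compares protein synthesis and breakdown after consumption with the fasted state, which suggests a short metabolic test rather than weeks of use. All of this stands. It limits the likely size but does not close the gap.

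**The taste mismatch affects everyone.** Lemon/lime against vanilla whey is a weakness of the blind for subjects with no prior exposure too, and removing prior EAA consumers leaves it in place. This is correct. Prior consumers are nonetheless the group for whom the plan's own safeguard fails by construction.

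**Prior whey users could recognise the comparator type.** Section 1.0 also reports that "Nine subjects received 12 weeks of dietary supplementation with 20 g of whey protein consumed daily". An exclusion limited to the EAA mixture would not reach them. That also stands, although the brand and flavour used in that pilot are not stated.

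**A stronger reading: carry-over into baseline.** A reader might infer that, because Section 4.2 sets no supplement-free interval before Visit 2, recent protein-supplement users would distort the baseline and cost power. The documents do not support this:

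- Both arms receive a protein or amino-acid product, so a prior user still contributes to the randomised comparison of EAA mixture with whey placebo.
- Randomisation balances prior use on average, and baseline is a covariate in Section 7.1.
- The commitment to refrain plausibly starts at consent, before the Visit 2 baseline.
- The whey pilot in Section 1.0 found no improvement in functional performance, which gives no ground for expecting a raised baseline.
- Any power loss would rest on an assumed share of users and an assumed loss of response, and the documents offer no basis for choosing a washout length.

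**Conclusion.** The point holds for unblinding through prior exposure. The plan admits past subjects, the product was studied locally before, no criterion excludes those who consumed it, and the protection against an acknowledged taste difference depends on ignorance of flavour.

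The conclusion rests on two assumptions: that some past EAA subjects are on the call-back list and otherwise eligible, and that the product they were given tasted enough like the present lemon/lime one to be recognised. Both are plausible; neither is documented. The number affected could be zero, and the size of any bias is unknown. The expected direction, if recognition acts through expectation, favours the EAA mixture.

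This is an eligibility gap worth closing because closing it is cheap. It does not show that the trial will be biased, and it is not the whole of the blinding problem.

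**What to change.** Add one item to Section 4.2 excluding anyone who has consumed the EAA mixture, under any trade name, in an earlier study. The trade-name wording matters because the figure caption in Section 1.0 labels the product UpBeat, while the rest of the protocol calls it the EAA mixture. Filter call-back lists from earlier EAA studies before subjects are phoned, and ask about earlier EAA studies at Visit 1 so that the criterion also applies to clinic referrals.

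The cost is a short eligibility amendment and a slightly smaller call-back pool. No visit, test or analysis is added. The change does not cure the difference in taste for subjects without prior exposure, which has to be dealt with separately.
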